6.2.1 Acalabrutinib

No additional preparation and handling are required for acalabrutinib.

6.2.2 Chlorambucil

No additional preparation and handling are required for chlorambucil.

Chlorambucil will be obtained by the investigational sites and labelled locally if required. See local prescribing information for further instructions regarding recommended storage conditions and packaging configuration.

6.2.3 Rituximab

6.2.3.1 Preparation/handling

The antibody is formulated for intravenous injection as a sterile product in a solution of sodium chloride (pH 6.5) containing polysorbate 80 and sodium citrate. Rituximab is packaged in 10 mL (100 mg) and 50 mL (500 mg) pharmaceutical-grade glass vials at a concentration of 10 mg protein per mL.

Rituximab should be stored in a secure refrigerator at 2°-8°Celsius (36°-46°Fahrenheit). Do not freeze or store at room temperature. The product is a protein – HANDLE GENTLY AND AVOID FOAMING, as this may lead to the de-naturing of the product proteins.

All transfer procedures require strict adherence to aseptic techniques, preferably in a laminar flow hood. Prepare rituximab solution as follows:

- Refrigerate (2°-8°C [36°-46°F]) all materials and solutions prior to use.
- Use sterile, non-pyrogenic disposable containers, syringes, needles, stopcocks, and transfer tubing etc.

- Transfer of rituximab from the glass vial should be made by using a suitable sterile graduated syringe and large gauge needle.
- Transfer the appropriate amount of rituximab from the graduated syringe into a partially filled IV pack containing sterile pyrogen-free 0.9% sodium chloride solution (saline solution). Mix by inverting the bag gently. **DO NOT USE A VACUUM APPARATUS** to transfer the product from syringe to the plastic bag.
- Place an IV administration into the outflow port of the bag containing the infusion solution
- NOTE: **DO NOT USE** evacuated glass containers which require vented administration sets because this causes foaming as air bubbles pass through the solution.
- The administration of rituximab will be accomplished by slow IV infusion. **CAUTION: DO NOT ADMINISTER AS AN IV PUSH OR BOLUS.**
- Do not infuse concomitantly with another IV solution or IV medications.

6.2.3.2 Storage

Rituximab should be stored in a secure refrigerator at 2-8°C (36-46°F). Refer to local label for further instruction regarding recommended storage condition.

6.3 Measures to minimise bias: randomisation and blinding

All subjects will be centrally/regional/local assigned to randomised study treatment using an Interactive Response Technology/Randomisation and Trial Supply Management (IRT/RTSM). Before the study is initiated, the telephone number and call-in directions for the IRT and/or the log-in information and directions for the RTSM will be provided to each site.

If a subject withdraws from the study, then his/her enrollment/randomisation code cannot be reused. Withdrawn subjects will not be replaced.

This is an open-label study. To maintain the integrity of the study, AstraZeneca personnel directly involved in the study conduct will refrain from accessing treatment records whenever possible, and under no circumstances will they view data aggregated by treatment arm during the course of the study. The site will contact the IRT/RTSM prior to the start of study treatment administration for each subject. The site will record the treatment assignment on the applicable case report form, if required. Potential bias will be reduced by central randomization. One randomization list will be produced for each of the randomization strata. A blocked randomization will be generated, and all centers will use the same list in order to minimize any imbalance in the number of patients assigned to each treatment group.

6.4 Treatment compliance

The investigational product should only be used as directed in this protocol. Details of treatment with investigational product including: change from the dosing schedule, does interruptions, dose reductions, dose discontinuations should be recorded in eCRF.

The investigational product will not be distributed to the study site until the contract is concluded between the study site and the sponsor. The investigator or designee is responsible for managing the IMP from time of receipt by the study site until the destruction of all unused IMP at that site. The investigator(s) is responsible for ensuring that all unused IMP is returned to the site by the subject(s).

6.4.1 Acalabrutinib

For acalabrutinib taken in the clinic, subjects should take the dose from the drug dispensed to them for that particular time period. Subjects will receive a drug diary to record the specific time each dose was taken and to record reasons for any missed doses.

Subject compliance will be assessed at each study visit. The subject will be instructed to bring the diary and any remaining capsules to the clinic at their next visit. The study staff will review the diary and ask the subject if all of the capsules were administered. Any remaining or returned capsules will be counted and recorded in accountability records. Returned capsules must not be re-dispensed to another subject.

6.4.2 Chlorambucil

Accountability and subject compliance will be assessed by maintaining adequate “drug dispensing” and return records.

Subjects will be asked to return all used and unused chlorambucil containers at the end of the treatment as a measure of compliance.

A Drug Dispensing Log must be kept current and should contain the following information:

- Identification of the subject to whom the study medication was dispensed
- Date(s) and quantity of the study medication dispensed to subject
- Date(s) and quantity of chlorambucil returned by the subject

6.4.3 Rituximab

Subject can only return to site for IV infusion of rituximab. Treatment compliance will be assured by reconciliation of site drug accountability logs.

6.5 Concomitant therapy

Any medication or vaccine including over-the-counter or prescription medicines, vitamins, and/or herbal supplements that the subject is receiving at the time of 4 weeks prior to starting study treatment and all concomitant treatments during the study through 30 days after the last dose of all study drugs must be recorded in the electronic Case Report Form (eCRF) along with:

- Reason for use (indication)
- Dates of administration including start and end dates
- Dosage information including dose, frequency and route

After a subject discontinues study treatment, receipt of all subsequent anticancer therapies to treat CLL will be collected in survival follow-up.

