A central imaging service will be used to provide independent radiologic assessments for the purposes of the primary endpoint. All imaging assessments (including unscheduled visit scan) will be sent to the sponsor appointed central reader on an ongoing basis. Assessment of scans by BICR will be triggered only upon investigator-assessed progression for both arms and the BICR confirmation will be reported back to sites. If the BICR does not confirm disease progression, tumor assessments should be continued in line with the schedule of assessments. Since the primary analysis of the study is based on BICR, it is important that study treatment and scheduled imaging assessments continue until progression confirmed by BICR. After the final analysis and per Amendment 5.0, disease progression can be assessed by investigator.

If at the time of primary PFS analysis it is identified that a patient has disease progression by BICR that has not been identified by the investigator, the sponsor will contact the investigator to discuss whether continued treatment with study medication is appropriate.

The investigator must evaluate the response of the subject per IWCLL criteria (see Table 10).

Table 10 Response Assessment Criteria for CLL (modified from Hallek 2018) – IWCLL Criteria

Group	Parameter	CR a	PR b	PD	SD
A	Lymph nodes	None ≥ 1.5 cm	Decrease $\geq 50\%$ (from baseline) c	Increase $\geq 50\%$ from baseline or from response	Change of -49% to +49%
	Liver and/or spleen size d	Spleen size < 13 cm; liver size normal	Decrease $\geq 50\%$ (from baseline)	Increase $\geq 50\%$ from baseline or from response	Change of -49% to +49%
	Constitutional symptoms	None	Any	Any	Any
	Circulating lymphocyte count	Normal	Decrease $\geq 50\%$ from baseline	Increase $\geq 50\%$ over nadir with absolute count $\geq 5 \times 10^9/L$	Change of -49% to +49%
B	Platelet count	$\geq 100,000/\mu L$	$\geq 100,000/\mu L$ or increase $\geq 50\%$ over baseline	Decrease of $\geq 50\%$ from baseline secondary to CLL	Change of -49% to +49%
	Hemoglobin	≥ 11.0 g/dL (untransfused and without erythropoietin)	≥ 11 g/dL or increase $\geq 50\%$ over baseline	Decrease of ≥ 2 g/dL from baseline secondary to CLL	Increase < 11.0 g/dL or $< 50\%$ over baseline, or decrease > 2 g/dL
	Marrow	Normocellular, no CLL cells, no B-lymphoid nodules	Presence of CLL cells, or of B-lymphoid nodules, or not done	Increase of CLL cells by $\geq 50\%$ on successive biopsies	No change in marrow infiltrate

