##### Sustained hematologic improvement

Sustained hematologic improvement is defined as hematologic improvement that persisted continuously for  $\geq 56$  days (8 weeks) without blood transfusion or growth factors. This sustained improvement requires that 1) two assessments meet the improvement criteria and are at least 56 days apart, 2) all assessment(s) with non-missing data between those two assessments must meet the improvement criteria, and 3) there is no concomitant use of blood transfusion/growth factor during this time period. The proportion of subjects achieving sustained hematologic improvement in the subset of subjects with cytopenia(s) at baseline, prior to subsequent anticancer therapy, will be summarized by treatment arm.

Cytopenia is defined as at least one of the following 3 criteria being met:

- Neutropenia:  $ANC \leq 1.5 \times 10^9/L$
- Anemia:  $Hgb \leq 11 \text{ g/dL}$
- Thrombocytopenia: platelet count  $\leq 100 \times 10^9/L$ .

Hematologic improvement in the subset of patients with cytopenia(s) is defined as follows for each parameter:

- Improvement to hemoglobin  $> 11 \text{ g/dL}$  from baseline or increase  $\geq 50\%$  over baseline.
- Improvement to platelet counts  $> 100 \times 10^9/L$  from baseline or increase  $\geq 50\%$  over baseline.
- Improvement to  $ANC > 1.5 \times 10^9/L$  or increase  $\geq 50\%$  over baseline.

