#### **4.2.8 Concomitant and other treatments**

Information on any treatment within the four weeks prior to initiation of study drug and all concomitant treatments given up to 30 days after discontinuation of study drug, or objective disease progression (whichever is later), with reasons for the treatment, will be recorded in the eCRF. Thereafter, only subsequent regimens of anti-cancer therapy will be recorded in eCRF.

Other anti-cancer therapies, investigational agents, and radiotherapy should not be given while the patient is on study drug.

Medications received prior to, concomitantly, or post-treatment will be coded using the WHODrug Dictionary Anatomical Therapeutic Chemical (ATC) Classification codes. Concomitant medications will be summarized for the FAS by ATC classification codes.

For the purpose of inclusion in prior and/or concomitant medication or therapy summaries, incomplete medication or radiotherapy start and stop dates will be imputed as detailed in [Section 4.2.4](#).

Prior medications, concomitant and post-randomized treatment medications are defined based on imputed start and stop dates as follows:

- Prior medications are those taken prior to study drug with a stop date prior to the first dose of study drug.
- Concomitant medications are those with a stop date on or after the first dose date of study drug (and could have started prior to or during treatment).
- Post-treatment medications are those with a start date after the last dose date of study drug.

In addition, all post-treatment anti-cancer therapies will be summarized for the full analysis set.

The following summaries will be produced:

- Summary of concomitant medications
- Summary of Post study drug cancer therapies

All concomitant and other treatment data will be listed.

Missing coding terms should be listed and summarized as "Not coded".

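### Protocol 6.5 and SAP 4.2.8 end concomitant-treatment recording at different times, so late transfusion or growth-factor support in Arm B may be missed in the descriptive hematologic-improvement summary

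*Protocol*

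**What the plan says.** **Recording period, protocol.** Section 6.5 requires that "all concomitant treatments during the study through 30 days after the last dose of all study drugs must be recorded". Once a subject is off treatment, it adds only that "receipt of all subsequent anticancer therapies to treat CLL will be collected in survival follow-up".

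**Recording period, SAP.** Section 4.2.8 describes the eCRF as holding "all concomitant treatments given up to 30 days after discontinuation of study drug, or objective disease progression (whichever is later"), and then says: "Thereafter, only subsequent regimens of anti-cancer therapy will be recorded in eCRF". SAP section 6, which lists departures from the protocol, mentions the China analysis sets and the nodular PR clarification but not this.

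**The output that needs the data.** SAP 4.2.2.9 defines sustained hematologic improvement for patients with cytopenia at baseline. It requires that "two assessments meet the improvement criteria and are at least 56 days apart", that every non-missing count in between also qualifies, and that "there is no concomitant use of blood transfusion/growth factor during this time period". The proportion achieving this, "prior to subsequent anticancer therapy, will be summarized by treatment arm".

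**Treatment and follow-up.** Protocol 4.1 and 6.1.2 limit rituximab plus chlorambucil to six 28-day cycles, with chlorambucil on Days 1 and 15. Acalabrutinib continues to progression or another discontinuation criterion. Protocol Table 2 and section 7.1.2 keep Arm B hematology and disease evaluation going after treatment ends. Section 6.5.1 permits hematopoietic growth factors.

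**The concern.** The no-support condition in SAP 4.2.2.9 can be checked only where support is recorded. The condition applies up to subsequent anticancer therapy, but the protocol's recording rule is tied to the last dose. Arm B stops by design after six cycles and Arm A does not, so the same rule gives the two arms different observation periods for the same condition.

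A transfusion or growth factor that nobody was asked to record reads as absent. A late Arm B count held up by support would then pass as sustained improvement, whereas a comparable interval in an Arm A patient still on drug would be disqualified. What is at stake is the fairness of one by-arm proportion, with the error in Arm B's favor. The window stated in the SAP would largely close the gap, but the protocol is the document that instructs sites.

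**Working it through.** The plan states no figure on this point, so there is none to reproduce. The check is calendar arithmetic on 28-day cycles, with Cycle 1 Day 1 as day 1.

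**1. When Arm B recording ends under Protocol 6.5**
- Last rituximab, Cycle 6 Day 1: 5 × 28 + 1 = day 141.
- Last chlorambucil, Cycle 6 Day 15: 5 × 28 + 15 = day 155.
- Full course, no delay: 155 + 30 = day 185, or 184 / 30.4375 = 6.0 months after day 1.
- If the Cycle 6 Day 1 rituximab is the last dose of either drug: 141 + 30 = day 171 (5.6 months).
- With one 4-week delay: 155 + 28 + 30 = day 213 (7.0 months).

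**2. What is still covered**
- Protocol Table 2 schedules post-baseline Arm B hematology on days 8, 15, 22, 29, 36, 43, 57, 85, 113, 141 and 169. All 11 fall before day 185.
- A 56-day span is fully recorded if it starts by 185 − 56 = day 129.
- On scheduled counts, the last such pair is Cycle 5 Day 1 (day 113) to Cycle 7 Day 1 (day 169): 169 − 113 = 56 days.

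**3. What is not covered**
- The next scheduled count is Cycle 10 Day 1: 9 × 28 + 1 = day 253.
- Cycle 7 Day 1 to Cycle 10 Day 1 is 253 − 169 = 84 days, of which 185 − 169 = 16 are recorded and 253 − 185 = 68 are not.
- Every later interval (Cycle 10 to 13, days 253 to 337, and onward) is wholly outside the window.

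**4. How much Arm B follow-up lies beyond day 185**
- Protocol 9.2 assumes exponential PFS with a 30-month Arm B median, so λ = ln 2 / 30 = 0.0231 per month.
- Progression-free at 6.045 months: exp(−0.0231 × 6.045) = 0.87.
- Expected progression-free time up to t is (1 − exp(−λt)) / λ. Up to 6.045 months this is 5.64 months.
- With uniform 30-month accrual and analysis at 45 months (Protocol 4.4), follow-up runs from 15 to 45 months and the average is 21.2 months. The unrecorded share is 1 − 5.64 / 21.2 = 73%.
- With analysis at 53 months (Protocol 9.2), follow-up runs from 23 to 53 months and the average is 24.9 months. The unrecorded share is 1 − 5.64 / 24.9 = 77%.

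These are shares of time, not of misclassified patients.

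**5. Size of the error**

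Neither document gives the rate of late support in Arm B or the improvement rate, so this step is an assumption. Let p be the true improvement proportion and q the share of true non-improvers miscounted as improved. The apparent proportion is p + (1 − p)q.

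| True p | Apparent, q = 2% | Apparent, q = 20% |
|---|---|---|
| 40% | 41.2% | 52% |
| 60% | 60.8% | 68% |
| 80% | 80.4% | 84% |

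**The case against.** The strongest reply is that the consequence is small and partly conjectural. Most of it stands.

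- **Descriptive output.** Sustained hematologic improvement is not among the formal analyses in SAP Table 7 and has no test. An error in Arm B's favor also works against acalabrutinib. This stands.
- **Early improvers are safe.** One qualifying 56-day span is enough, and Arm B counts are frequent before day 185. Only patients who have not already qualified, and who later reach the threshold on unrecorded support, can be miscounted. This stands.
- **Time is not bias.** A reader might take the 73% to 77% of time, or the fact that six of the eight response evaluations through Cycle 25 fall after day 185, as the size of the bias. The documents do not support that, because neither is a misclassification rate.
- **Complete response.** The CR hemoglobin criterion in Protocol Table 10 requires a value "untransfused and without erythropoietin", so a reader might infer that late Arm B CRs cannot be verified. SAP 3.2 says responses are assigned by BICR or the investigator and not derived by program, and the investigator has the source records. That inference should be dropped.
- **Arm A is not always covered.** A patient who stops acalabrutinib without progressing meets the same 30-day cutoff. The asymmetry is by design in Arm B and incidental in Arm A.
- **Actual data capture is unknown.** The eCRF is not among the documents, and the concomitant-medication rows of Protocol Tables 1 and 2 are not legible in the available text. SAP 4.2.8 may describe what the form really holds. If so, the practical effect disappears and only the conflict in wording remains.

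The adverse event form is not a dependable substitute. Protocol 8.3.2 records whether an event was treated, but Table 13 ends routine AE reporting 30 days after the last dose, leaving related SAEs and AEs of concern.

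**Conclusion.** The two documents contradict each other on how long concomitant treatments are recorded, and the SAP does not declare the difference. If sites follow Protocol 6.5, Arm B transfusion and growth-factor use after about day 185 (full course, no delays) need not be recorded, while Arm A is recorded as long as acalabrutinib continues. Late, supported Arm B improvements can then be miscounted as sustained, overstating Arm B in a descriptive, untested summary.

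The size cannot be derived from the documents; the table in the working is an illustration under assumed rates. A reader might infer that the between-arm result is known to be biased. The documents support only that it can be, depending on what the eCRF captured and how many Arm B patients improved late with support. PFS does not use this condition, and the subsequent anticancer therapy that drives its censoring is collected under both texts.

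The point is worth correcting because it is cheap to correct.

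**What to change.** Reconcile Protocol 6.5 with SAP 4.2.8 so that, in both arms, transfusions and hematopoietic growth factors are recorded until progression or the start of subsequent anticancer therapy, using visits already scheduled. If the eCRF already does this, say so in both documents.

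If the data were collected only to 30 days after the last dose:

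1. In SAP 4.2.2.9, count only improvement intervals that lie wholly within each patient's own recorded period. A fixed day 185 would not do this, because patients who stop early lose recording sooner and those with delayed doses keep it longer.
2. Add a supportive summary over a common early window in both arms, for example through Cycle 7 Day 1.
3. The protocol synopsis states that the 03Jan2024 cutoff became the final analysis and that the study was unblinded. Label the common-window summary as post hoc if it is added after that, and report the reason in the CSR.

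The cost is slightly more data entry in Arm B follow-up or, for the fallback, a shorter assessment span that leaves out genuine late improvements.

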6.5.1 Permitted concomitant therapy

Antiemetics are permitted if clinically indicated. Standard supportive care medications are permitted as per institutional standards. Use of hematopoietic growth factors is permitted per Consensus of Chinese Experts (Version 2015). Primary prophylactic use of myeloid growth factors (e.g., granulocyte colony-stimulating factor [G-CSF]) is not allowed according to the guideline.

For subjects considered at risk for tumor lysis syndrome: administer appropriate hydration and allopurinol or rasburicase per institutional standards before initiating treatment.

For subjects at risk for infections: bacterial/viral/fungal prophylaxis is allowed per institutional standards.

Short course use of steroids (≤ 2 weeks) >20 mg/day is permitted for premedication use, or to manage infusion-related reactions or to manage other inflammatory reactions, such as asthma exacerbation. During study participation, subjects may also receive systemic or enteric corticosteroids at any required dosage as needed for treatment-emergent comorbid conditions.

6.5.2 Prohibited concomitant therapy

Any concurrent chemotherapy (e.g., bendamustine, cyclophosphamide, pentostatin, or fludarabine), anticancer immunotherapy (e.g., obinutuzumab, alemtuzumab, or ofatumumab), corticosteroids (at dosages equivalent to prednisone >20 mg/day), kinase inhibitors (e.g., ibrutinib, zanubrutinib, and idelalisib), bone marrow transplant, experimental therapy, and radiotherapy for treating CLL are prohibited. Localized, short courses of radiotherapy are allowed for the treatment of lesions unrelated to the disease under study, if approved by the study physician. Should a subject develop a second primary malignancy while on trial, the subject should be managed according to institutional guidelines with diagnostic evaluations as clinically indicated, and it may be necessary for subjects to permanently discontinue study treatment. Continuation of acalabrutinib treatment should be discussed with the study physician.

The concomitant use of strong inhibitors/inducers of CYP3A with acalabrutinib should be avoided when possible (see [Appendix H](#)). If a subject requires short-term treatment with a strong CYP3A inhibitor (such as anti-infectives for up to 7 days), interrupt acalabrutinib

treatment. Refer to [Table 7](#) for dose modifications due to required short-term use of moderate CYP3A inhibitors.

Warfarin or equivalent vitamin K antagonists (e.g., *phenprocoumon*) are prohibited.

Administration of herbal medication during study treatment period is not recommended, unless it is prescribed by the investigator for treatment of specific clinical events. Use of proton-pump inhibitors, H2 receptor antagonists, or antacids while taking acalabrutinib has the potential to decrease acalabrutinib exposure. If treatment with a gastric acid reducing agent is required, consider using a H2-receptor antagonist (2 hours after acalabrutinib) or antacid (2 hours before or 2 hours after acalabrutinib). Avoid coadministration with proton-pump inhibitors.

**Table 7 Instructions for Coadministration of Drugs with Acalabrutinib
 Coadministered Drug**

Instructions for Coadministration of Drugs with Acalabrutinib Coadministered Drug	Acalabrutinib
Strong CYP3A inhibitor	Avoid concomitant use with acalabrutinib. If the inhibitor will be used short-term (such as anti-infectives for up to 7 days), interrupt acalabrutinib.
Moderate CYP3A inhibitor	No dose adjustment. Monitor patients closely for adverse reactions if taking moderate CYP3A inhibitors.
Mild CYP3A inhibitor	No change
Strong CYP3A inducer	Avoid concomitant use. If a subject requires treatment with a strong CYP3A inducer, increase the acalabrutinib dose to 200 mg BID during concomitant administration with the strong inducer and return to recommended dose of 100 mg BID after stopping the strong CYP3A inducer.
Moderate CYP3A inducer	No change
P-gp inhibitor	No change
BCRP inhibitor	No change
Narrow therapeutic index P-gp substrate	No change
Bile acid sequestrants	No change
Statin (OATP substrate)	No change
Proton pump inhibitors	Avoid concomitant use.
H2-receptor antagonists	Take acalabrutinib 2 hours before taking a H2-receptor antagonist.
Antacids	Separate dosing by at least 2 hours.

